## Introduction

Acute kidney injury (AKI) is a complex disorder characterized by a rapid decline in renal function, leading to the accumulation of metabolic waste products and fluid imbalance. It is a frequent and severe complication among critically ill patients, affecting approximately 30–50% of those admitted to intensive care units (ICUs). This syndrome

is associated with increased morbidity, mortality, and healthcare costs.

The prognosis of AKI depends on its severity and underlying cause. The worst outcomes are observed in patients who require renal replacement therapy (RRT), in whom mortality approaches 60%. AKI is often secondary to non-renal organ dysfunction such as sepsis, respiratory failure, or heart failure. These conditions may reduce renal perfusion and promote inflammation and oxidative stress, resulting in kidney injury.

Although the KDIGO consensus criteria provide a standardized definition of AKI based on changes in serum creatinine (SCr) and urine output (UO), these markers tend to appear late and lack sensitivity for early detection. Moreover, survivors of AKI have been shown to face a markedly increased risk of infections, particularly within the first three months after hospital discharge. This heightened susceptibility is mainly due to a state of multifactorial immunosuppression and cellular anergy.

### Background

Following an episode of AKI, infections are a frequent complication.

In a retrospective Spanish cohort, infection surveillance began three months after the AKI episode. Over a median follow-up of nine months (IQR 2–56), 153 patients (42%) developed at least one infection. The most common were urinary tract infections [67 (44%)], respiratory tract infections [46 (30%)], soft tissue infections [14 (9%)], and abdominal infections [14 (9%)]. No specific baseline variable was associated with infection type.

Factors linked to infection during follow-up were analyzed using Cox regression. In univariate analysis, the following were associated with infection risk: older age [HR 1.18 (95% CI, 1.05–1.33),  $P = 0.005$ ], cognitive impairment [HR 1.51 (95% CI, 1.00–2.28),  $P = 0.050$ ], lower eGFR three months post-AKI [HR 0.91 (95% CI, 0.86–0.97),  $P = 0.002$ ], decline in eGFR from baseline to three months [HR 1.07 (95% CI, 1.01–1.14),  $P = 0.028$ ], and transition from AKI to chronic kidney disease (CKD) [HR 1.55 (95% CI, 1.13–2.14),  $P = 0.007$ ].

Baseline eGFR differed significantly between patients who developed infection and those who did not ( $P = 0.038$ ), although the nadir and post-AKI eGFR values were similar between groups ( $P = 0.289$  and  $P = 0.215$ , respectively).

## Problem Definition

### Study Rationale:

- Infections represent a serious yet understudied complication among patients who have experienced acute kidney injury (AKI). While kidney disease is known to increase susceptibility to infections—and infections are a major cause of mortality in this population—the precise relationship between AKI and infection risk, as well as the immunologic mechanisms underlying this vulnerability, remain poorly understood.
- Existing data indicate that postoperative AKI is associated with higher rates of infection-related hospitalizations, and that the transition from AKI to chronic kidney disease (CKD) further amplifies infectious risk. However, to date, no studies have evaluated the efficacy of antibiotic prophylaxis in preventing infections among patients recovering from severe AKI after hospital discharge.
- This research gap underscores the need for a clinical trial aimed at determining whether prophylactic administration of trimethoprim-sulfamethoxazole can reduce infection incidence in this high-risk group.

### Research Question:

Does administration of trimethoprim-sulfamethoxazole 800/160 mg every 48 hours for 90 days reduce the risk of infections in patients who have experienced severe acute kidney injury after hospital discharge?

### Justification

The justification for this study lies in the absence of previous clinical trials evaluating the effectiveness of antibiotic prophylaxis in reducing infection risk following acute kidney injury (AKI) among discharged patients. Identifying infections as one of the most underestimated complications in AKI highlights the urgent need to address this research gap. Implementing a clinical trial to evaluate the administration of trimethoprim-sulfamethoxazole could provide crucial data regarding its efficacy and contribute to improving medical care and health outcomes in this vulnerable population.

The significance of this study is reflected in its potential to influence clinical practice and improve the management of AKI patients. Reducing infections may not only decrease morbidity but also enhance quality of life and lessen the healthcare system's burden. As the first study of its kind, its findings could establish a precedent for future research and guide the development of antibiotic prophylaxis protocols in similar clinical contexts.

The feasibility of the study is supported by its design—a randomized, double-blind, placebo-controlled clinical trial—which aligns with current recommendations for addressing AKI. The selection of Hospital Civil de Guadalajara “Fray Antonio Alcalde” as the research center ensures access to a relevant AKI patient population. Furthermore, clearly defined inclusion criteria and randomization methods suggest adequate planning to ensure successful recruitment and adherence to the protocol.

Potential vulnerabilities of the study include the possibility of bias during randomization or outcome assessment, as well as limited generalizability of findings to other populations due to cultural, socioeconomic, or healthcare delivery differences. Additionally, since this study targets a critically ill population, adverse

events related to antibiotic use will represent an important consideration. Addressing these aspects is essential for the validity and interpretation of the study's findings.

### Theoretical and Conceptual Framework

Infections are among the least studied consequences of AKI. Although kidney diseases are well-recognized risk factors for infections—and infections remain one of the leading causes of death among patients with renal disease—the underlying mechanisms of this secondary immunodeficiency remain poorly defined [Steiger S]. Regarding the bidirectional relationship between AKI and infections, the recently published NARA-AKI prospective study demonstrated that postoperative AKI in non-cardiac surgery was associated with increased hospitalizations due to infections [Tagawa M, Kellum JA]. Beyond AKI, patients with chronic kidney disease (CKD) are more vulnerable to infections and exhibit worse outcomes than cohorts without CKD [Xu H, Su G]. Interestingly, not only the progression from AKI to CKD but also the decline in eGFR—*independent* of baseline or post-AKI eGFR—was independently associated with infection risk.

Several mechanisms may explain this increased susceptibility to infection. The immune dysfunction of CKD—characterized by impaired innate and adaptive immunity, decreased clearance of proinflammatory cytokines, and even epigenetic modifications in hematopoietic stem cells—adds to the alterations seen in AKI, such as disrupted kidney-immune system crosstalk, changes in immune cell composition and function, and an exaggerated inflammatory response [LaFavers K, Syed-Ahmed M]. Nevertheless, the precise pathophysiology of the elevated infection risk in patients transitioning from AKI to CKD remains incompletely understood.

Finally, a retrospective cohort study (Griffin BR) showed that recovery from AKI was associated with a 4.5-fold increase in the likelihood of infection (OR 4.53 [95% CI, 2.43–8.45];  $p < 0.0001$ ) within 30 days after hospital discharge. Moreover, the association between AKI and subsequent infection remained significant at 31–60 days and 91–365 days post-discharge, but not during the 61–90-day interval.

### Study Objectives

#### Primary Objective:

To reduce the risk of infections within 90 days following hospital discharge after a severe episode of acute kidney injury (AKI).

#### Secondary Objectives:

To evaluate the risk of rehospitalization, infection-related rehospitalization, septic shock, major adverse kidney events (MAKE) at 90 days, incidence of hyperkalemia, and new episodes of acute kidney injury. Adverse events (AEs) will be coded using the Medical Dictionary for Regulatory Activities (MedDRA) and classified as mild, moderate, or severe. AEs of special interest include skin rash, erythema, nausea, vomiting, headache, and tachycardia.

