### Materials and Methods

- This study will be a phase 2, randomized, prospective, double-blind, investigator-initiated, parallel-group, placebo-controlled clinical trial conducted at the Hospital Civil de Guadalajara “Fray Antonio Alcalde”, Guadalajara, Mexico. All patients with AKI receiving nephrology consultation will be considered for inclusion.
- The diagnosis of AKI will follow the Kidney Disease: Improving Global Outcomes (KDIGO) serum creatinine criteria. In accordance with the recommendations of the 31st Acute Disease Quality Initiative Group regarding the design of clinical trials for AKI treatments, the subphenotype of patients at the highest risk of post-AKI infections will be selected. This study will be considered a phase 2 randomized, double-blind, placebo-controlled trial meeting efficacy (AKI trajectory and eGFR evaluation), feasibility (patient recruitment and protocol adherence), and safety (adverse events and drug reactions) objectives.
- Group randomization will be performed using the clinical trial randomization tool available at <http://www.winepi.net/f108.php>, employing traditional block randomization. Sequences for each arm and stratum will be generated using maximal asymptotic randomization.
- Patients will be recruited on an outpatient basis to document any infectious event of any kind occurring within the first 90 days, as well as cases of rehospitalization due to infection within the same period at the Hospital Civil de Guadalajara “Fray Antonio Alcalde”.

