### Observation Unit

Patients diagnosed with severe AKI will be monitored for a period of 90 days after hospital discharge. Each participant will be evaluated based on infection incidence, rehospitalization, adverse events, and other health outcomes related to trimethoprim–sulfamethoxazole administration. Observation will focus on collecting clinical data and health outcomes specific to each participant.

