#### Elimination Criteria

- Patients who partially or completely discontinue the prophylactic antibiotic before completing three months of treatment
- Patients rehospitalized for non-infectious causes within the first three months
- Patients who take a different dose of prophylactic antibiotic than prescribed

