## Operationalization of Variables

### Independent Variable:

- Treatment: Administration of the study drug versus placebo (categorical variable with two levels: active treatment or placebo).

Dependent Variables (Primary Outcomes):

- Development of gastrointestinal infections — categorical nominal binary variable (yes/no)
- Development of upper respiratory infections — categorical nominal binary variable (yes/no)
- Development of lower respiratory infections — categorical nominal binary variable (yes/no)
- Development of urinary tract infections — categorical nominal binary variable (yes/no)
- Development of soft tissue infections — categorical nominal binary variable (yes/no)
- Rehospitalization due to infection — categorical nominal binary variable (yes/no)
- Development of septic shock — categorical nominal binary variable (yes/no)
- Requirement for long-term renal replacement therapy — categorical nominal binary variable (yes/no)
- Death from any cause — categorical nominal binary variable (yes/no)
- Progression to chronic kidney disease or  $\geq 50\%$  decline in eGFR — categorical nominal binary variable (yes/no)
- Worsening renal function with  $\geq 25\%$  decline in eGFR due to infection — categorical nominal binary variable (yes/no)
- Presence of hyperkalemia — categorical nominal binary variable (yes/no)
- Adverse drug reactions — categorical nominal variable

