#### Statistical Analysis

An intention-to-treat approach will be adopted, including all randomized participants who receive the intervention, for both primary and secondary outcomes.

Categorical variables will be expressed as counts and percentages (%) and compared using either the chi-square test or Fisher’s exact test, as appropriate.

Continuous variables will be reported as median values (IQR), since normal distribution is not expected according to the Shapiro–Wilk test; between-group comparisons will be performed using the Mann–Whitney U test.

A repeated-measures analysis of variance (ANOVA) will be used to compare variables over time between groups. A Kaplan–Meier survival curve will be plotted for both groups and compared using the log-rank test. Missing data will be imputed using the mean linear interpolation method.

All statistical tests will be two-tailed, and a p-value < 0.05 will be considered statistically significant.

The analyses and figures will be performed using MedCalc software (Version 22.0.21, Ostend, Belgium) and GraphPad Prism (Version 10.2.3, Boston, Massachusetts, USA).

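### Any-cause rehospitalisation and new AKI are secondary objectives without a variable, and the rule eliminating non-infectious readmissions is not reconciled with intention-to-treat

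*Protocol*

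**What the plan says.** - **Objectives** (Protocol, Secondary Objectives): "To evaluate the risk of rehospitalization, infection-related rehospitalization, septic shock, major adverse kidney events (MAKE) at 90 days", then "incidence of hyperkalemia, and new episodes of acute kidney injury". Rehospitalisation and infection-related rehospitalisation are separate items, so the first is naturally read as rehospitalisation for any cause. New AKI is not limited to infectious causes.
- **Events to be documented** (Materials and Methods): infectious events, "as well as cases of rehospitalization due to infection within the same period".
- **Variables** (Operationalization of Variables): the only readmission item is "Rehospitalization due to infection — categorical nominal binary variable (yes/no"). The only item for a smaller acute fall in kidney function is a 25% or greater "decline in eGFR due to infection". The other kidney items are long-term renal replacement therapy and progression to CKD or an eGFR decline of at least 50%.
- **General statement** (Observation Unit): "Each participant will be evaluated based on infection incidence, rehospitalization, adverse events, and other health outcomes". Rehospitalisation is unrestricted here but not defined.
- **Elimination** (Elimination Criteria): "Patients rehospitalized for non-infectious causes within the first three months".
- **Analysis population** (Statistical Analysis): "An intention-to-treat approach will be adopted, including all randomized participants who receive the intervention, for both primary and secondary outcomes".

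**The concern.** Two stated objectives have no variable to answer them. One of them, rehospitalisation for any cause, is also affected by a rule that takes patients out of the study because they had part of that outcome. The event happens after randomisation and treatment may influence it: the protocol itself expects antibiotic-related adverse events and lists hyperkalaemia and new AKI among its objectives.

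At stake is the net-benefit question. A prophylactic antibiotic may lower infectious admissions and raise others. Only a count of all readmissions shows whether the total fell, stayed level or rose.

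**Working it through.** **Step 1. Objectives against variables.**

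| Secondary objective | Matching variable |
|---|---|
| Rehospitalisation | None |
| Infection-related rehospitalisation | Rehospitalisation due to infection |
| Septic shock | Septic shock |
| MAKE at 90 days | Long-term RRT; death; CKD progression or at least 50% eGFR decline |
| Hyperkalaemia | Hyperkalaemia |
| New AKI | None; the nearest item requires the decline to be due to infection |

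A new AKI episode from a non-infectious cause that recovers, or stays short of the 50% decline or CKD, meets no kidney item in the list.

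**Step 2. The plan's own figure.** The only number needed from the protocol is the arm size, 60 (Sample Size). For 59% against 29.5%, two-sided 0.05 and 90% power, the pooled-variance formula is

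n = [1.96·√(2·p̄(1−p̄)) + 1.2816·√(p₁(1−p₁) + p₂(1−p₂))]² / (p₁−p₂)², with p̄ = 0.4425.

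This gives (1.377 + 0.860)² / 0.295² ≈ 57.5, so 58 per group. Power at 60 per group is 91.2%. The stated 60 is close enough to serve as the arm size below; the concern does not depend on it.

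**Step 3. If the elimination rule governs.** Let I be patients with an infectious readmission and N those with a non-infectious one, in an arm of 60, each readmitted patient being readmitted once.

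- Any-cause risk, everyone kept: (I + N)/60.
- Any-cause risk after elimination: I/(60 − N). Infection-related risk after elimination is the same expression, so the two objectives coincide by construction.

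The protocol gives no readmission rates, so I and N are assumptions. Four sets, placebo then active, with risk ratios as active over placebo:

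| Case | I | N | Any-cause, all kept | RR | After elimination | RR |
|---|---|---|---|---|---|---|
| a | 12, 6 | 6, 12 | 18/60, 18/60 | 1.00 | 12/54, 6/48 (22.2%, 12.5%) | 0.56 |
| b | 12, 6 | 6, 18 | 18/60, 24/60 | 1.33 | 12/54, 6/42 (22.2%, 14.3%) | 0.64 |
| c | 12, 8 | 3, 9 | 15/60, 17/60 | 1.13 | 12/57, 8/51 (21.1%, 15.7%) | 0.75 |
| d | 12, 9 | 3, 6 | 15/60, 15/60 | 1.00 | 12/57, 9/54 (21.1%, 16.7%) | 0.79 |

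**Step 4. Where the apparent benefit comes from.** With everyone kept, the infection-related risk ratio in case a is (6/60)/(12/60) = 0.50, and elimination moves it to 0.56, slightly towards 1. The apparent reduction is therefore the infectious effect assumed at the outset, left standing alone once the non-infectious readmissions are gone. What goes wrong is that it would stand as the any-cause result.

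**Step 5. If intention-to-treat governs.** Nobody is removed and the denominators stay at 60. The listed readmission variable still counts only I, so N is not reported and new AKI remains without a variable.

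**Side effect.** If elimination took 10%, 20% or 30% of each arm (54, 48 or 42 left), power at 59% against 29.5% would fall from 91% to 88%, 84% or 79%. No allowance for this is stated.

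**The case against.** The strongest reply has four parts.

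- **Intention-to-treat is promised.** A reader might infer that the plan removes every patient readmitted for a non-infectious cause. The documents do not support that: the Statistical Analysis section adopts intention-to-treat for primary and secondary outcomes. What they show is a conflict, and the selection effect is conditional on elimination prevailing. This stands.
- **The data may be collected anyway.** The Observation Unit section names rehospitalisation without restriction. Applying the elimination rule requires each readmission to be found and classified. The methods adopt the KDIGO creatinine criteria. So the gap is shown in the definition of variables, not in the capture of data. This also stands. Derivation details of secondary endpoints can be left to an analysis plan. Here, however, the protocol itself narrows what is documented and listed to infection-related readmission, against its own objective.
- **Harm is recorded elsewhere.** A reader might infer that a harmful drug would necessarily look beneficial. Hyperkalaemia, adverse drug reactions, death and renal decline are all variables, and adverse events are to be MedDRA-coded and graded, so harm could show. That is right, with two limits: none of these gives the total of readmissions, and if elimination is applied, patients admitted for such harms leave the analysis with their data.
- **The counts are chosen.** A reader might take the near-halving in case a as bias created by elimination. It is not, as step 4 shows. The counts illustrate direction and mechanism and estimate nothing about this trial.

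**Conclusion.** The point holds in a limited form. Without any assumption: rehospitalisation for any cause and new AKI are secondary objectives, neither has a variable, and the elimination rule conflicts with the intention-to-treat statement. Conditional on elimination governing: the any-cause objective cannot be answered, and an excess of non-infectious readmissions on active drug is removed from view. The size shown (true risk ratio 1.00 to 1.33, reported 0.56 to 0.79) rests on assumed counts with more non-infectious readmissions on active drug, one readmission per readmitted patient, and 60 per arm. If intention-to-treat governs, there is no selection, only the missing variables. Deleting the elimination rule alone would therefore not repair the objectives. The documents do not support the claim that the plan is certain to remove these patients or to hide all harm.

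**What to change.** 1. In Operationalization of Variables, add two dated yes/no variables: rehospitalisation for any cause within 90 days of discharge, with its main cause; and new AKI by the KDIGO serum creatinine criteria already adopted in Materials and Methods. Keep rehospitalisation due to infection as the cause-specific subset.
2. In Materials and Methods, state that all rehospitalisations are documented, with cause.
3. Reconcile Elimination Criteria with Statistical Analysis: analyse non-infectious readmission as an outcome in all randomised patients, and use the elimination list at most to define a per-protocol sensitivity set.

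The cost is protocol wording and two added fields. The data are to be extracted from the hospital's electronic record, post-discharge creatinine is already required for inclusion, and the elimination rule already presupposes that non-infectious readmissions are identified. The change is best made before data collection, since readmissions that were never recorded may be hard to recover later.

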### Working Hypothesis

Hypothesis: Administration of trimethoprim–sulfamethoxazole 800/160 mg every 48 hours for 90 days reduces the risk of infections.

Null Hypothesis: Administration of trimethoprim–sulfamethoxazole 800/160 mg every 48 hours for 90 days does not reduce the risk of infections.

### Materials and Methods

- This study will be a phase 2, randomized, prospective, double-blind, investigator-initiated, parallel-group, placebo-controlled clinical trial conducted at the Hospital Civil de Guadalajara “Fray Antonio Alcalde”, Guadalajara, Mexico. All patients with AKI receiving nephrology consultation will be considered for inclusion.
- The diagnosis of AKI will follow the Kidney Disease: Improving Global Outcomes (KDIGO) serum creatinine criteria. In accordance with the recommendations of the 31st Acute Disease Quality Initiative Group regarding the design of clinical trials for AKI treatments, the subphenotype of patients at the highest risk of post-AKI infections will be selected. This study will be considered a phase 2 randomized, double-blind, placebo-controlled trial meeting efficacy (AKI trajectory and eGFR evaluation), feasibility (patient recruitment and protocol adherence), and safety (adverse events and drug reactions) objectives.
- Group randomization will be performed using the clinical trial randomization tool available at <http://www.winepi.net/f108.php>, employing traditional block randomization. Sequences for each arm and stratum will be generated using maximal asymptotic randomization.
- Patients will be recruited on an outpatient basis to document any infectious event of any kind occurring within the first 90 days, as well as cases of rehospitalization due to infection within the same period at the Hospital Civil de Guadalajara “Fray Antonio Alcalde”.

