### Study Population

Patients diagnosed with severe acute kidney injury (AKI) who have been discharged from the hospital and receive nephrology follow-up at the Hospital Civil de Guadalajara “Fray Antonio Alcalde”, Guadalajara, Mexico. This group will include patients with diverse demographic and clinical characteristics who meet the inclusion criteria established in the study protocol.

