#### Control Group Definition

The control group will include patients who, during hospitalization at the Old Civil Hospital of Guadalajara “Fray Antonio Alcalde”, were identified by the Nephrology Service as having severe acute kidney injury that had resolved or was in the process of recovery. These patients will have been discharged with standard post-AKI management and care, without the addition of antibiotic prophylaxis.

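### Materials and Methods gives the phase 2 efficacy objective as AKI trajectory and eGFR and omits infection, contradicting the primary objective and hypothesis; the primary-outcome list does not settle which counts

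*Protocol*

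**What the plan says.** The protocol states its purpose in several places.

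- **Materials and Methods**, on the phase 2 design: the trial is "meeting efficacy (AKI trajectory and eGFR evaluation), feasibility (patient recruitment and protocol adherence), and safety (adverse events and drug reactions) objectives". The efficacy part names two kidney items and no infection.
- **Materials and Methods**, last bullet: "Patients will be recruited on an outpatient basis to document any infectious event of any kind occurring within the first 90 days".
- **Primary Objective**: "To reduce the risk of infections within 90 days following hospital discharge after a severe episode of acute kidney injury (AKI".
- **Working Hypothesis**: "Administration of trimethoprim–sulfamethoxazole 800/160 mg every 48 hours for 90 days reduces the risk of infections". The null hypothesis is its negation. The Research Question also asks about infection.
- **Secondary Objectives** lists rehospitalization, infection-related rehospitalization, septic shock, major adverse kidney events (MAKE) at 90 days, hyperkalemia and new AKI.
- **Operationalization of Variables** lists 13 dependent variables, all under a heading that calls them primary outcomes. Three concern the kidney: long-term renal replacement therapy, progression to CKD or an eGFR fall of at least 50%, and an eGFR fall of at least 25% due to infection.
- **Study Population**: "Patients diagnosed with severe acute kidney injury (AKI) who have been discharged from the hospital and receive nephrology follow-up". Control Group Definition describes controls "as having severe acute kidney injury that had resolved or was in the process of recovery".
- **Statistical Analysis** makes all tests two-tailed at p < 0.05, gives no order among outcomes, and plans a repeated-measures ANOVA for variables over time without naming the variables.

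**The concern.** The protocol says in two different ways what would count as efficacy. The objective and hypothesis say infection; the phase 2 description says kidney course. Because Operationalization of Variables calls both kinds of outcome primary, a reader cannot use that list to decide between them.

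The ambiguity matters once results are known. If infections did not differ but an eGFR comparison did, Materials and Methods would support calling the eGFR result efficacy. If infections fell and eGFR did not differ, the same text could be used to say that the efficacy objective was missed. A later analysis plan may add detail, but the conflict over the objective lies in the protocol itself.

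AKI trajectory also fits the design poorly. Patients are studied after discharge, when the in-hospital part of the index episode is over.

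**Working it through.** No calculation decides this point. The check sets the sections side by side and asks what the sample size was built for.

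**1. Which sections name infection as the question?** The Research Question, Primary Objective and Working Hypothesis do. Sample Size names one event, infection after AKI, at about 30%. Materials and Methods itself selects the patients at highest risk of post-AKI infection and recruits to document infections. Only its efficacy parenthesis names something else. That parenthesis presents a kidney assessment as efficacy, while Secondary Objectives ranks MAKE and new AKI second.

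**2. Do the outcome definitions settle it?** Of the 13 variables under the primary-outcome heading, five are infections by site (gastrointestinal, upper respiratory, lower respiratory, urinary, soft tissue). Two are infection consequences (rehospitalization due to infection, septic shock). Three are kidney outcomes. The other three are death, hyperkalemia and adverse drug reactions: 5 + 2 + 3 + 3 = 13. None is defined as AKI trajectory, and the two eGFR items are yes/no thresholds. Septic shock, infection-related rehospitalization and hyperkalemia are secondary in Secondary Objectives but primary here. The list does not resolve the conflict.

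**3. What was the trial sized for?** Inputs from Sample Size: 59% against 29.5%, 95% confidence, 90% power, 60 per group. With pooled variance in both terms:

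n = (1.960 + 1.282)² × 2 × 0.4425 × 0.5575 / 0.295² = 10.51 × 0.4934 / 0.0870 = 59.6, rounded up to 60.

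Here 0.4425 is the mean of 0.59 and 0.295. The stated figure is reproduced as a comparison of two proportions. (Pooling under the null only gives 58; power at 60 per group is 91.2%.)

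The same section then gives a difference of 0.8 with SD 1.5 and Zβ = 0.84: n = 2 × (1.96 + 0.84)² × 1.5² / 0.8² = 35.28 / 0.64 = 55.1, rounded up to 56. It names no variable or unit, so it cannot be read as an eGFR or trajectory effect. No effect on either is specified anywhere. (The mismatch between 30% and 59%, and between the two power levels, is a separate matter.)

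**4. What can the timing support?** Recruitment is outpatient and the population is already discharged. Sampling Method says candidates are identified on hospital rounds, but no dosing before discharge is described. Taking treatment to start at or after discharge, it cannot affect the in-hospital course of the index AKI. Kidney function over the following 90 days can be compared: Inclusion Criteria requires creatinine after discharge, some patients may still be recovering, and MAKE, new AKI, CKD progression, renal replacement and eGFR decline are all planned outcomes.

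**The case against.** The strongest reply is that the parenthesis is a loose description of a phase 2 trial, not a decision rule. It names no endpoint, test or success threshold. The formal statements are the Primary Objective and the Working Hypothesis, both about infection, and the text around the parenthesis points to infection twice. This stands in part: the intended objective can be recovered. But the parenthesis is the only place that spells out efficacy for the phase 2 design, and the primary-outcome heading and unranked p < 0.05 rule do nothing to override it.

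A second reply is that eGFR and the post-AKI course are measurable after discharge. This stands in full. A reader might infer from post-discharge entry that the trial cannot answer any kidney question. The documents do not support that: required creatinine follow-up, patients possibly still recovering, and the listed kidney outcomes all allow a comparison over 90 days. Only the in-hospital course of the index AKI is out of reach. The remark about AKI still in recovery is also written for the control group alone.

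A reader might also infer a definite inflation of the false-positive rate from having two efficacy definitions. The protocol does not define such a pair of tests. Independence between them would be doubtful too, since one eGFR outcome is by definition due to infection. No such figure is claimed here.

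**Conclusion.** The contradiction holds and should be corrected. One statement of the efficacy objective omits infection and names kidney outcomes, against three formal statements and the only event named in the sample-size text. The outcome list adds to the conflict by calling three kidney variables primary. Together with the unranked significance rule, this leaves room to choose the efficacy result after the data are seen.

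The size is qualitative: 0 of 13 variables is defined as AKI trajectory, 3 of 13 are kidney outcomes labelled primary, and no eGFR or trajectory effect is specified for sizing. The conclusion assumes that the objective and hypothesis state the real intent and that treatment starts at or after discharge. It does not say that kidney outcomes are uninformative, only that they are mislabelled as the efficacy objective.

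**What to change.** In **Materials and Methods**, replace the efficacy parenthesis with: efficacy (any infection within 90 days of discharge). Delete AKI trajectory, and label eGFR and MAKE outcomes as secondary, in line with Secondary Objectives. State that the efficacy conclusion rests on infection alone.

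In **Operationalization of Variables**, change the heading so that only infection is primary. List the kidney, renal replacement, death, hyperkalemia and adverse-reaction variables as secondary or safety outcomes. Septic shock and infection-related rehospitalization should follow Secondary Objectives. The section lists infection only by site, so add any infection as one yes/no variable; otherwise the revised objective has no matching outcome. Editing Materials and Methods alone would leave the kidney variables labelled primary.

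The cost is wording in these two sections. Infections of any kind are already to be documented, so no data, visits or patients are added.
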